**Table 7-2: Dosing during fallback option**

Dose arm	Fallback
PSL 400mg bid	PSL 300mg bid
PSL 200mg bid	PSL 150mg bid
PSL 100mg bid	PSL 75mg bid
Placebo	Placebo

bid=twice daily; PSL=padsevonil

After fallback, the dose will be kept stable for the duration of the Maintenance Period. Further titration is not allowed.

### 7.2.2 Taper Period

The Taper Period, in case of withdrawal or completion of the study, will comprise 3 weeks as presented in [Table 7-3](#). A faster or slower taper schedule than the suggested 3 weeks may be implemented if medically necessary, as per the Investigator's medical judgment. During the Taper Period, the dose of PSL must always be administered as bid morning and evening doses, approximately 12 hours apart. Concomitant AED dosages should be kept stable throughout the entire study including the Taper Period.

Subjects should be monitored during the Taper Period for withdrawal symptoms, including behavioral changes, withdrawal-related AEs, or rebound seizures, as well as the severity of the CIWA-B withdrawal scores. Medical treatment may be required for the management of severe withdrawal symptoms. Additional AEDs (excluding prohibited medications) may be added and/or changes to dose regimens of concomitant AEDs are permitted if medically necessary as per the Investigator's medical judgment to manage rebound seizures.

**Table 7-3: Taper Period dosing**

Dose Arm	Dose in mg per intake (morning-evening) during taper a				
	Week 16	Week 17		Week 18	
PSL 400mg bid	300-300	200-200	150-150	100-100	50-50
PSL 300mg bid					
PSL 200mg bid	200-200				
PSL 150mg bid	150-150	100-100		50-50	
PSL 100mg bid	100-100				
PSL 75mg bid	75-75				
Placebo	1-1 PBO-PBO				

bid=twice daily; PBO=placebo; PSL=padsevonil

Taper steps may vary in length by  $\pm 3$  days per week.

a Taper Period for subjects who choose an early discontinuation may occur before Week 16.

### 7.2.3 Conversion Period

In case the subjects wish to proceed to the OLE study, the treatments and doses will be adjusted gradually in a blinded way to reach the single-entry dose into the OLE study (PSL 200mg bid) as presented in Table 7-4. During the Conversion Period, the dose of IMP must always be administered as bid morning and evening doses, approximately 12 hours apart. Subjects who agree to proceed to the OLE study and begin the Conversion Period but later decide not to participate in the OLE study will need to complete the IMP taper process during the first weeks of the OLE study (EP0093) before withdrawing from the EP0093 study.

Subjects taking placebo will be converted to active PSL.

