**Table 7-4: Conversion Period dosing**

Dose Arm	Dose in mg per intake (morning-evening) during conversion		
	Week 16	Week 17	Week 18
PSL 400mg bid	300-300	200-200	
PSL 300mg bid			
PSL 200mg bid	200-200		
PSL 150mg bid			
PSL 100mg bid	100-100	150-150	200-200
PSL 75mg bid			
Placebo	50-50	100-100	150-150 a

bid=twice daily; OLE=open-label extension; PSL=padsevonil

Dose adjustments steps may vary in length by  $\pm 3$  days per week while overall Conversion Period length should not change by more than 1 week.

a After completion of Week 18, the dose will be 200-200, the entry dose in the OLE study, EP0093.

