the entry dose for the OLE. Subjects who took placebo during the Maintenance Period will receive PSL titrated to the target dose.

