3 DATA ANALYSIS CONSIDERATIONS

3.1 General presentation of summaries and analyses

Statistical analysis and generation of tables, figures, subject data listings, and statistical output will be performed using SAS Version 9.3 or higher. All tables and listings will use Courier New font size 9.

Descriptive statistics will be displayed to provide an overview of the study results. For categorical variables, the number and percentage of subjects in each category will be presented. Unless otherwise noted, all percentages will be displayed to 1 decimal place. No percentage will be displayed for zero counts, and no decimal will be presented when the percentage is 100%. For continuous variables, descriptive statistics will include number of subjects with available measurements (n), mean, SD, median, minimum, and maximum.

Decimal places for descriptive statistics will always apply the following rules:

- “n” will be an integer

- Mean, SD, and median will use one additional decimal place compared to the original data
- Minimum and maximum will have the same number of decimal places as the original value.

Unless otherwise specified, statistical tests of efficacy variables will be presented as two-sided p values rounded to three decimal places. P-values less than 0.001 will be presented as “<0.001” and p-values greater than 0.999 will be presented as “>0.999.” Statistical comparisons will be two-sided and will be performed at the 0.05 level of significance.

A complete set of data listings containing all documented data as well as calculated data (e.g., change from Baseline), as applicable, will be generated.

Treatment groups will be displayed as: Placebo, PSL 100mg bid, PSL 200mg bid, and PSL 400mg bid.

Log-transformation is based on natural logarithm. For analyses on log-transformed values, model estimates will be back-transformed to anti-log space for table presentation. See Section 8.1.1 for details.

Data collected at scheduled visits will be included in the by-visit summary. Data collected at unscheduled visits will not be included in the by-visit summary, but will be considered when determining the Last Visit, minimum, and maximum post-Baseline values during the Treatment Period. Data collected on Visit 8 will be summarized separately for subjects in the Conversion Period versus the Taper and Safety FU Period.

In general, all CRF data will be presented in the subject listings.

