3.6 Treatment assignment and treatment groups

At Baseline, eligible subjects will be randomly assigned to treatment regimens as described in Section 2.3. Prior to unblinding, the study team should identify and review all cases in which subjects received an incorrect study drug (dosing errors resulting in treatment crossover). Note that while dispensing errors can be identified prior to unblinding, actual treatment crossovers can only be identified via IRT report (only identifying the subject number), or after unblinding.

The FAS will be the primary analysis set for all efficacy summaries and analyses. Treatment crossover Subjects (including any subjects with dosing errors) will be analyzed for efficacy according to their randomized treatment assignment and not the actual treatment received.

Safety analyses will be based on the SS. It is expected that subjects will receive the randomized treatment and be analyzed according to that assigned treatment. However, if a subject were to experience a dosing error resulting in treatment crossover, incorrectly treated subjects will be evaluated during the blinded data evaluation meetings to assess the potential impact of such cases and any special considerations for statistical analyses.

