10 SAFETY ANALYSES

The SS will be used to summarize and analyze all safety variables. In case of dosing administration error, summaries and analyses using the SS will be conducted according to actual treatment administered according to the rule described in Section 3.6. Safety data will be summarized for each treatment group and the PSL total group.

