10.2 Adverse events

Adverse events are recorded on the AE CRF as they occur, from the time informed consent is granted until study completion or study termination (end of the SFU period 30 days after the last IMP intake). All AEs will be coded using the latest available version of MedDRA.

A treatment-emergent adverse event (TEAE) is defined as any event not present prior to the initiation of the first dose of study treatment or any unresolved event already present before initiation of the first dose that worsens in intensity following exposure to the treatment. The number and percentage of subjects who experience TEAEs at any time during the study will be summarized by SOC and PT. The following tabular summaries will be presented for the SS:

- Incidence of TEAEs during the Treatment Period – Overview. Of note, the corresponding table is required for data transparency reporting.
- Incidence of TEAEs by period (Treatment Period, Titration and Stabilization Period, Maintenance Period, Conversion Period, and Taper and SFU Period)
- Incidence of Serious TEAEs by period (Treatment Period, Titration and Stabilization Period, and Maintenance Period)
- Incidence of TEAEs leading to discontinuation by period (Treatment Period, Titration and Stabilization Period, and Maintenance Period)
- Incidence of TEAEs leading to dose reduction during the Stabilization Period

The following will be presented for TEAEs during the overall Treatment Period:

- Subject numbers for TEAEs
- Incidence of TEAEs occurring in at least 5% of subjects in any treatment group
- Incidence of TEAEs occurring in at least 2% of subjects in any PSL group and greater than placebo group
- Incidence of TEAEs by Relationship
- Incidence of TEAEs by Maximum Intensity
- Incidence of SAEs by Relationship. Of note, the corresponding table is required for data transparency reporting.
- Incidence of Fatal TEAEs by Relationship. Of note, the corresponding table is required for data transparency reporting.

- Incidence of Non-Serious TEAEs above the threshold of 5% of subjects in any treatment group. Of note, the corresponding table is required for data transparency reporting.
- Summary of the duration in days per event for the following TEAEs: somnolence, dizziness, fatigue, irritability and headache. In this analysis, if an AE is ongoing, the duration will be calculated till the date of final contact.

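### As written, the SAP's Conversion Period safety tables show placebo subjects who have started PSL under Placebo and leave them out of PSL total

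*Protocol*

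**What the plan says.** Both documents state that placebo subjects who choose the open-label extension receive active drug during Conversion. Protocol 7.2.3: "Subjects taking placebo will be converted to active PSL". SAP 2.5.1: "Subjects who took placebo during the Maintenance Period will receive PSL titrated to the target dose". Protocol Table 7-4 gives the placebo row three weekly steps of 50, 100 and 150mg per intake, and its footnote adds: "After completion of Week 18, the dose will be 200-200, the entry dose in the OLE study, EP0093".

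The SAP's display and assignment rules are:

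- SAP 3.1: "Treatment groups will be displayed as: Placebo, PSL 100mg bid, PSL 200mg bid, and PSL 400mg bid".
- SAP 10: "Safety data will be summarized for each treatment group and the PSL total group".
- SAP 3.6, on safety: "It is expected that subjects will receive the randomized treatment and be analyzed according to that assigned treatment".
- SAP 3.5.3 and 10: actual treatment replaces assigned treatment only where a dosing error occurred.

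Two provisions bring Conversion data into summary tables. SAP 10.2 lists "Incidence of TEAEs by period (Treatment Period, Titration and Stabilization Period, Maintenance Period, Conversion Period, and Taper and SFU Period". SAP 3.1 says of the visit that ends Conversion: "Data collected on Visit 8 will be summarized separately for subjects in the Conversion Period versus the Taper and Safety FU Period".

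**The concern.** In Conversion, the column headed Placebo would contain data only from people who have just begun PSL, and the column headed PSL total would not contain those people. Protocol 2.4 describes adverse events as dose-related and as tending to ease within the first days of dosing. Former placebo subjects are the only group in this period starting PSL from zero, so effects of first exposure are most likely to appear in them. Under the SAP's labels those effects sit in the comparator column. SAP 10.2 also orders AE tables by frequency in the PSL total column, so a term seen mainly in these new starters would be ranked without them.

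What is at stake is the correct reading of the Conversion safety outputs. The randomized comparison is not at stake.

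**Working it through.** The plan gives no figure to reproduce. The check sets its rules side by side, with simple arithmetic on Table 7-4.

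**1. What converted placebo subjects take.** From the placebo row of Table 7-4, over 3 nominal weeks (the table allows each step to vary in length):

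- Mean dose = (50 + 100 + 150)/3 = 100mg bid, equal to the lowest randomized PSL dose.
- Cumulative dose = 7 days × 2 intakes × (50 + 100 + 150)mg = 4200mg over 21 days.
- Dose in the last week before Visit 8, relative to the lowest randomized dose = 150/100 = 1.5.

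The other three arms also take PSL, so 0 of 4 arms are on placebo in Conversion.

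**2. Which column the SAP gives them.** There are four possible routes:

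- *Assigned treatment (3.6).* This gives Placebo.
- *Actual treatment (3.5.3, 10).* This is available only for a dosing error. A planned conversion is not an error.
- *A further column.* SAP 3.1 lists four groups and SAP 10 adds PSL total. Neither has a column for subjects moving from placebo to PSL.
- *A rule specific to Conversion.* The Visit 8 provision in 3.1 separates subjects by period, not by treatment taken. The list of changes from the protocol (SAP 3.9) adds nothing on this.

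Only the first route applies. A subject classed as Placebo is then outside PSL total.

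**3. Which outputs are affected.** Protocol 8.3.2 schedules all four Visit 8 domains for converting subjects.

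| Output | SAP section | Basis |
|---|---|---|
| TEAEs, Conversion Period | 10.2 | named period |
| Laboratory, Conversion Visit 8 | 10.3 | by scheduled visit |
| Vital signs, Conversion Visit 8 | 10.4.1 | by scheduled visit |
| ECG, Conversion Visit 8 | 10.4.2 | by scheduled visit |
| Psychiatric and mental status, Conversion Visit 8 | 10.4.4.3 | by scheduled visit |

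That makes 1 + 4 = 5 outputs. SAP 16 repeats each for Japan and non-Japan.

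**4. What is not affected.** Table 3-1 ends the Treatment Period at Visit 7, before Conversion begins. Efficacy, Treatment Period safety tables, and placebo subjects who taper without converting are therefore untouched.

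**The case against.** The strongest reply is that the SAP never says outright that these subjects appear under Placebo. SAP 10.2 defers AE table layout to the sponsor's standard formats and to those used in the PSL program. Protocol 2.3 shows that the completed Phase 2 study reported a placebo/PSL group. The shells may therefore already have the right column. That is possible, but the sentence does not assign these subjects anywhere, and it does not reach the four Visit 8 summaries.

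A second reply is that display by randomized arm is a consistent convention. In Conversion the 400mg arm steps down to 200mg bid and the 100mg arm rises to it, so every label then denotes the original arm. Both documents also disclose the conversion. This stands in part: an informed reader could work out what the column means. But the PSL arms stay on PSL and inside PSL total, whereas the Placebo label is wrong about whether drug was taken at all. The AE listing shows daily dose at onset, which helps a reader of listings but does not correct the tables.

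A reader might also infer more than the text supports:

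- *That the overall PSL–placebo safety difference is diluted.* SAP 2.3.1 defines incidence over the entire study, and 10.2 mentions events at any time. Yet every table itemized in 10.2 is limited to a named period, and none pools Conversion events into a whole-study contrast.
- *That follow-up after conversion is contaminated.* Protocol 7.2.3 sends subjects who change their minds to taper within EP0093. Table 3-1 has a date rule for tapering after conversion, but no count stands behind it.
- *That exposure reporting singles out this group.* SAP 10.1 stops at 16 weeks for every arm.
- *That a known share of PSL-treated subjects is missing from PSL total.* With r the placebo conversion rate divided by the PSL rate, the share is r/(r + 3). Equal rates give 1/4 = 25%. Assumed rates of 50% to 90% in either direction give 0.5/(0.5 + 3×0.9) = 16% to 0.9/(0.9 + 3×0.5) = 38%. The documents give no conversion rates, so no percentage is claimed.

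**Conclusion.** The point holds for five named outputs: the Conversion TEAE table and four Conversion Visit 8 summaries. In each, the SAP's rules place subjects taking PSL under Placebo and outside PSL total. The conclusion rests on reading 3.1, 3.6, 3.5.3 and 10 together and on treating planned conversion as something other than a dosing error. The nominal exposure is material at a mean of 100mg bid for three weeks, but the number of converters and any effect on observed incidences cannot be derived from the documents.

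Conversion to PSL is not itself criticized. Efficacy and the randomized safety comparison through Visit 7 stand as planned. The priority is a minor to moderate SAP correction.

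**What to change.** In SAP 3.1 and 10, show placebo subjects who convert in a separate Placebo/PSL column for data from the day after Visit 7, the date on which Table 3-1 starts Conversion. For Conversion data, either count them in PSL total or label that total as excluding them.

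If an entire-study TEAE or SAE table is produced, end placebo attribution at Visit 7 for subjects who convert and show their later events under Placebo/PSL. Subjects who never convert keep placebo attribution through Taper and Safety Follow-up.

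The cost is one extra column and one date rule, programmed from dates and doses already collected. The protocol, visit schedule, IRT and drug supply do not change. The drawback is that a PSL total including these subjects mixes new starters with people already 16 weeks on drug, so the separate column should be kept in either case.

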**Table 7-4: Conversion Period dosing**

Dose Arm	Dose in mg per intake (morning-evening) during conversion		
	Week 16	Week 17	Week 18
PSL 400mg bid	300-300	200-200	
PSL 300mg bid			
PSL 200mg bid	200-200		
PSL 150mg bid			
PSL 100mg bid	100-100	150-150	200-200
PSL 75mg bid			
Placebo	50-50	100-100	150-150 a

bid=twice daily; OLE=open-label extension; PSL=padsevonil

Dose adjustments steps may vary in length by  $\pm 3$  days per week while overall Conversion Period length should not change by more than 1 week.

a After completion of Week 18, the dose will be 200-200, the entry dose in the OLE study, EP0093.

### 7.3 Packaging

Padsevonil tablets are manufactured, packaged, and labeled according to Good Manufacturing Practice (GMP) guidelines and applicable laws or regulations.

The IMP will be provided in blister-packed treatment cards, each providing 3, 4, or 7 days' treatment of active or placebo (plus some reserve tablets in case of unexpected event).

#### **7.4 Labeling**

Clinical drug supplies will be labeled in accordance with the current International Council for Harmonisation (ICH) guidelines on Good Clinical Practice (GCP) and GMP and will include any locally required statements. If necessary, labels will be translated into the local language.

#### **7.5 Handling and storage requirements**

The Investigator (or designee) is responsible for the safe and proper storage of IMP at the site. Investigational medicinal product stored by the Investigator is to be kept in a secured area with limited access according to the storage conditions mentioned on the label.

Appropriate storage conditions must be ensured either by controlling the temperature (eg, room, refrigeration unit) or by completion of a temperature log in accordance with local requirements on a weekly basis, including the capture of minimum and maximum temperatures reached over the time interval.

In case an out-of-range temperature is noted, it must be immediately reported as per instructions contained in the IMP Handling Manual.

The Investigator (or designee) will instruct the subject to store the IMP following the instructions on the label.

#### **7.6 Drug accountability**

A Drug Accountability form will be used to record IMP dispensing and return information on a by-subject basis and will serve as source documentation during the course of the study. Details of any IMP lost, damaged (due to breakage or wastage), not used, partially used, disposed of at the study site, or returned to the Sponsor or designee must also be recorded on the appropriate forms. All supplies and pharmacy documentation must be made available throughout the study for UCB (or designee) to review.

The Investigator (or designee) is responsible for retaining all used, unused, and partially used containers of IMP until returned or destroyed.

The Investigator may assign some of the Investigator's duties for drug accountability at the study site to an appropriate pharmacist (or designee).

The Investigator must ensure that the IMP is used only in accordance with the protocol.

Periodically, and/or after completion of the clinical phase of the study, all used (including empty containers)/partially used, unused, damaged, and/or expired IMP must be reconciled and either destroyed at the site according to local laws, regulations, and UCB Standard Operating Procedures (SOPs) or returned to UCB (or designee). Investigational medicinal product intended for the study cannot be used for any other purpose than that described in this protocol.

#### **7.7 Procedures for monitoring subject compliance**

At each visit after IMP is dispensed and at the end of the Taper/Conversion Period, subjects must return all unused IMP and empty IMP containers. Drug accountability must be done in the

subject's presence in order to obtain explanations regarding discrepancies in compliance with the dosing regimen. Drug accountability must be recorded on the Drug Accountability form.

If a subject is found to be persistently noncompliant (defined as less than 75% or more than 125% compliant with the dosage schedule), the Sponsor, in conjunction with the Investigator, will make a decision as to whether the subject should be withdrawn from the study.

Timely completion of the subject diary is essential for evaluation of safety and efficacy. A caregiver is allowed to help the subject with the completion of the subject diary. Subject diary completion will be reviewed at each visit.

## **7.8 Concomitant medications/treatments**

### **7.8.1 Permitted concomitant treatments (medications and therapies)**

All subjects should continue to take their Baseline AED regimen (1 to 3 AEDs) unchanged over the whole study period. During the Taper Period, the Investigator is allowed to adjust AED dosing and/or add additional AED(s), only if medically necessary, based on his/her medical judgment.

- Drugs with possible CNS effects are allowed if at a stable dose from at least 1 month before Visit 1 and during the whole study period.
- Drugs with no CNS effects, and which are not strong CYP2C19 and/or CYP3A4 enzyme inducers/inhibitors or sensitive CYP2C19 substrates, are allowed. In cases of uncertainty, the Study Physician (or designee) should be contacted before initiating or stopping any medication during study unless it is a medical emergency. Although omeprazole is classified as a sensitive substrate, high doses of omeprazole have been well tolerated, and adjustment of the omeprazole dose is not generally required except with severe hepatic impairment and if long-term treatment is indicated. Therefore, omeprazole is permitted (see omeprazole prescribing information).
- Vigabatrin, retigabine, and felbamate are allowed and count as add-on AEDs
  - if taken for more than 2, 4, and 1 years, respectively, and
  - if requirements mentioned in the Exclusion Criteria (Section 6.2) are met.

